10.4 STATISTICAL ANALYSIS

10.4.1 General Considerations

The quantitative variables will be summarized using number of subjects (n), mean, median, standard deviation, minimum and maximum. The qualitative variables will be summarized using counts and percentages.

All summaries will be presented by treatment group. Summaries will be provided for demographics, baseline medical history, concurrent therapies, and subject disposition.

For the purpose of summarization, medical history, concurrent therapies, and adverse events will be coded to MedDRA and WHO Drug dictionaries, as appropriate.

Baseline measures are defined as the last measure prior to the initiation of study treatment, usually at Visit 2. If a measure is taken both pre-CAE® and post-CAE®, the baseline will be the time point matched value at Visit 2. For measures from daily subject diaries, baseline is defined as the average of all days during the run-in period. For changes from pre-CAE® to post-CAE® post first treatment, the change from pre-CAE® to post-CAE® at Visit 2 will be considered the baseline value.

All primary and secondary analyses will be 2-sided at a significance level of 0.05.

10.4.2 Unit of Analysis

Safety endpoints will be analyzed for both eyes. For efficacy endpoints, the unit of analysis will be the study eye, or the “worst eye,” as defined by the following:

Study Eye/Worst Eye: Eyes are eligible for analysis if they meet all of the inclusion criteria. In the case that both eyes are eligible for analysis, the worst eye will be the eye with worse (higher) inferior corneal staining pre-CAE® at Visit 2. If the inferior corneal staining is the same in both eyes, then the worst eye will be the eye with the highest

ocular discomfort pre-CAE® at Visit 2. If the ocular discomfort is the same in both eyes, then the right eye will be selected as the worst eye.

10.4.3 Missing Data

The primary efficacy analyses will be performed using Markov Chain Monte Carlo (MCMC) multiple imputation methodology for missing values. An analysis using observed data only will also be performed for the primary efficacy variables. As additional sensitivity analyses, Last Observation Carried Forward (LOCF) methodology and imputation via pattern mixture models will also be used to impute missing data for the analyses of the primary efficacy variables.

For the LOCF analyses of the primary efficacy variables at Day 57 (Visit 6), the last value from the previous visits will be carried forward, matching pre-CAE® or post-CAE® time points. A pre-CAE® time point will never be imputed for a post-CAE® value, and vice versa.

No secondary efficacy endpoints or safety endpoints will be imputed.

10.4.4 Multiplicity Consideration

For success, significance is required for both the primary sign and the primary symptom, and for both active treatments, hence no multiplicity adjustment is necessary.

10.4.5 Primary Efficacy Analyses

For both coprimary endpoints, pre-CAE® change from baseline will be calculated as visit – baseline such that a positive difference indicates a worsening of dry eye signs or symptoms. In addition, treatment comparisons between active and placebo will be calculated as active – placebo, such that a negative result indicates a better score for the active treatment (i.e., the active treatment had a smaller increase in dry eye signs or symptoms than the placebo group). The coprimary endpoints and changes from baseline will be summarized descriptively (n, mean, standard deviation, median, min and max) by visit and treatment group.

ANCOVA models will be used to compare the change from baseline in the pre-CAE® inferior corneal fluorescein staining at Day 57 (Visit 6), as measured on the Ora Calibra® scale, between each dose of 0.25% and 0.10% HL036 Ophthalmic Solution and Placebo. The ANCOVA models will include terms for baseline pre-CAE® inferior corneal fluorescein staining and study site. In addition, the study site by treatment interaction will be explored in a separate model to evaluate how the treatment effect may differ across study sites. As supportive analyses, two-sample t-tests and Wilcoxon rank sum tests will also be conducted. The primary analysis will use MCMC multiple imputation to have a full accounting of the ITT population at the Day 57 visit, as described in [Section 10.4.3](#).

Ocular dryness will be analyzed similarly. ANCOVA models will be used to compare the change from baseline in the pre-CAE® ocular discomfort score at Day 57 (Visit 6), as measured on the Ora Calibra® Ocular Discomfort Scale, between each dose of 0.25% and 0.10% HL036 Ophthalmic Solution and Placebo. The ANCOVA models will include terms for baseline (Visit 2) ocular discomfort and study site. In addition, the study site by treatment interaction will be explored in a separate model to evaluate how the treatment effect may differ across sites. As supportive analyses, two-sample t-tests and Wilcoxon rank sum tests will also be conducted.

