8.3.1 Visit 1: Day -14 ± 1 – CAE® Screening

All subjects will undergo the following screening assessments:

Pre-CAE®

- Informed Consent/HIPAA Prior to any changes in a subject's medical treatment and/or invasive procedures (e.g., controlled adverse environment), the study will be discussed with each subject and subjects wishing to participate must give written informed consent and sign a HIPAA form.
- Demographic Data and Medical/Medication/Ocular History Collect and record all demographic data, medical history, any medications and any underlying condition(s). Significant non-ocular medical history only within the past year and medications within the past 30 days will be captured. Record any medications the subject is taking, as well as those the subject may have taken but discontinued within 30 days prior to screening.
- Review of Inclusion/Exclusion Criteria
- Urine Pregnancy Test (for females of childbearing potential) Women of childbearing potential must have a negative urine pregnancy test to continue in the study.
- Ora Calibra® Ocular Discomfort Scale

- Ora Calibra® Ocular Discomfort and 4-Symptom Questionnaire Ocular Discomfort Score
- Ocular discomfort using a visual analog scale (VAS)
- OSDI®
- BCVA Utilizing an ETDRS Chart Subjects must have a score of [REDACTED] logMAR or better (Snellen equivalent score of [REDACTED]) in each eye at Visit 1.
- Slit Lamp Biomicroscopy A slit lamp exam will be performed at the beginning of the visit and again Post-CAE® to exclude subjects with disallowed ocular conditions.
- Conjunctival Redness Score An objective measure used to score redness on the Ora Calibra® Conjunctival Redness Scale for Dry Eye. Half point increments (0.5) may be used.
- TFBUT
- Corneal and Conjunctival Staining (fluorescein) as assessed by the Ora Calibra® Corneal and Conjunctival Staining Scale for Grading of Fluorescein Staining
- Corneal and Conjunctival Staining (lissamine green) as assessed by the Ora Calibra® Corneal and Conjunctival Staining Scale for Grading of Lissamine Green Staining
- Monitoring and Query AEs Report any AEs that occur after signing the ICF.

Screening Challenge (CAE® #1)

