10.3 SAMPLE SIZE

The primary objective of the study is to demonstrate a statistically significant difference between the active treatments and placebo.

This study is expected to enroll 50 subjects in each of the three treatment arms, for a total of 150 randomized subjects. Assuming a 10% drop out rate, 45 subjects per group are expected to complete the study.

Assuming a common standard deviation in the change from baseline for the pre-CAE® inferior corneal fluorescein staining of 0.72 units, a sample size of 45 subjects per group will have 90% power to detect a difference of 0.5 units between each of the active treatment groups and the placebo group using a two-sample t-test at a significance level of 0.05. A sample size of 45 subjects per treatment arm will have 90% power to detect a mean difference of 0.80 units in the change from baseline for the pre-CAE® ocular discomfort as assessed by the Ora Calibra® Ocular Discomfort Scale, assuming a standard deviation of 1.15 units. Using an analysis of covariance model (ANCOVA) for each primary endpoint should yield standard deviations no greater than those from a two-sample t-test. Therefore, the power for each endpoint for both the sign and the symptom is 81%, assuming independence between the endpoints. The power for both the sign and the symptom in both active treatments is 66%, assuming independence of treatments.

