## **9. General Statistical Considerations**

### **9.1 Unit of Analysis**

Safety endpoints will be analyzed for both eyes. For efficacy endpoints, the unit of analysis will be the study eye, or the “worst eye,” as defined by the following:

**Study Eye/Worst Eye:** Eyes are eligible for analysis if they meet all of the inclusion criteria. In the case that both eyes are eligible for analysis, the worst eye will be the eye with worse (higher) inferior corneal staining pre-CAE® at Visit 2. If the inferior corneal staining is the same in both eyes, then the worst eye will be the eye with the highest ocular discomfort pre-CAE® at Visit 2. If the ocular discomfort is the same in both eyes, then the right eye will be selected as the worst eye.

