After obtaining twenty complete data sets and calculating changes from baseline, the following SAS code will be used to run the ANCOVA model on each data set and combine the results from the twenty analyses:

```

PROC MIXED DATA = OUTDATA;
  BY _IMPUTATION_;
  CLASS TREATMENT SITE;
  MODEL CHANGE_INFERIOR = SITE BASELINE TREATMENT / SOLUTION COVB;
  LSMEANS TREATMENT / CL PDIFF;
  ODS OUTPUT LSMEANS = OUTLS DIFFS = OUTDIFFS;
RUN;
PROC SORT DATA=OUTLS; BY TREATMENT _IMPUTATION_; RUN;
PROC MIANALYZE DATA=OUTLS;
  BY TREATMENT;
  MODELEFFECTS ESTIMATE;
  STDERR STDERR;
RUN;

DATA OUTDIFFS;
  SET OUTDIFFS;
  COMPARISON = TREATMENT || ' - ' || LEFT(_TREATMENT);
RUN;
PROC SORT DATA=OUTDIFFS; BY COMPARISON _IMPUTATION_; RUN;
PROC MIANALYZE DATA=OUTDIFFS;
  BY COMPARISON;
  MODELEFFECTS ESTIMATE;
  STDERR STDERR;
RUN;

```

where

- *TREATMENT* is the name of the treatment group variable
- *SITE* is the site id
- *BASELINE* is the baseline pre-CAE® inferior fluorescein staining score in the study eye
- *CHANGE\_INFERIOR* is the pre-CAE® inferior fluorescein staining in the study eye at Visit 6 (Day 57 ± 3) – *BASELINE*
- *OUTLS* is the name of the output dataset that contains the statistical results for the treatment means from the ANCOVA model that is run on each of the twenty imputation datasets
- *OUTDIFFS* is the name of the output dataset that contains the statistical results for the differences in treatment means from the ANCOVA model that is run on each of the twenty imputation datasets

Similar SAS code will be used to conduct MCMC multiple imputation analysis for T-tests.

A sensitivity analysis will be performed on the ITT population using control-based pattern mixture model imputation. The SAS code for obtaining multiple pattern mixture model imputation data is:

```

PROC MI DATA = INDATA SEED = 386922 OUT = MDATA NIMPUTE = 1
  MINIMUM = 0 MAXIMUM = 4 ROUND = 0.5;

```

```

MCMC IMPUTE=MONOTONE;
VAR BASELINE INFERIOR;
RUN;

PROC MI DATA = MDATA SEED = 253464 OUT = OUTDATA NIMPUTE = 20
      MINIMUM = . . 0 0 MAXIMUM = . . 4 4 ROUND = . . 0.5 0.5;
CLASS SITE TREATMENT;
MONOTONE REG(INFERIOR = BASE SITE / DETAILS);
MNAR MODEL(INFERIOR / MODELOBS=(TREATMENT='Placebo')) ;
VAR SITE TREATMENT BASELINE INFERIOR;
RUN;

```

where

- *INDATA* is the name of the input dataset
- *MDATA* is the name an intermediary dataset with a monotone missing pattern
- *OUTDATA* is the name of the output dataset
- *TREATMENT* is the name of the treatment group variable

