#### 14.1.2 ORA CALIBRA® OCULAR DISCOMFORT SCALE

Ocular discomfort scores will be subjectively graded by the subjects using the Ora Calibra® Ocular Discomfort Scale at all scheduled visits. The ocular discomfort scale ranges from 0 to 4 [REDACTED]

[REDACTED]  
 [REDACTED].

Changes from baseline in the pre-CAE® Ocular Discomfort Scale will be summarized at Visit 6 (Day 57 ± 3) by treatment group for the study eye using quantitative summary statistics. Changes from baseline will be compared between each dose of 0.25% and 0.10% HL036 Ophthalmic Solution and placebo using an ANCOVA model that adjust for baseline and site. In addition, the study site by treatment interaction will be explored in a separate model to evaluate how the treatment effect may differ across study sites. In the case of a significant interaction at the 0.05 level, analyses will be performed by site to understand how the treatment effect differs across sites. The differences in means, two-sided 95% confidence intervals (CIs) for the difference in means and p-values will be reported. Pairwise t-tests from the ANCOVA model will be used to compare treatment and placebo groups. In addition, subjects in either active treatment group will be compared to the placebo group using a separate ANCOVA model. T-tests and Wilcoxon rank sum tests will also be conducted as sensitivity analyses to assess robustness of the results.

The primary analysis will use MCMC imputation on the ITT population at Visit 6 (Day 57 ± 3). SAS code for the multiple imputation analysis will resemble the code in Section 14.1.1. for pre-CAE® inferior fluorescein staining. Sensitivity analyses will be performed on the ITT and PP populations using observed data only, and on the ITT population using LOCF methodology and pattern mixture model imputation. The sensitivity analyses will include comparisons between treatment and placebo groups using ANCOVA models adjusting for site and baseline and t-tests. Observed data only (ITT and PP) and LOCF analyses will also include Wilcoxon rank sum tests.

Changes from baseline in the pre-CAE® Ocular Discomfort Scale in the study eye will be displayed graphically in a bar chart with standard error bars by visit and treatment group.

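### The primary ANCOVA leaves out the Visit 1 pre-CAE score of each co-primary endpoint: a valid analysis with a small, nearly free gain in precision not taken

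*Protocol*

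**What the plan says.** Protocol 10.4.5 sets out one ANCOVA per co-primary endpoint. For the sign: "The ANCOVA models will include terms for baseline pre-CAE® inferior corneal fluorescein staining and study site". For the symptom, the terms are the Visit 2 discomfort score and site. The SAP carries this into code in 14.1.1, "MODEL CHANGE_INFERIOR = SITE BASELINE TREATMENT / SOLUTION COVB", and describes the symptom model in 14.1.2 as an "ANCOVA model that adjust for baseline and site". The imputation step in SAP 14.1.1 uses two variables, the baseline and the Visit 6 score, and runs separately within each treatment-by-site cell.

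Visit 1 measures both endpoints before the CAE. Protocol 8.3.1 lists the Ocular Discomfort Scale and "Corneal and Conjunctival Staining (fluorescein) as assessed by the Ora Calibra® Corneal and Conjunctival Staining Scale" among the pre-CAE procedures. The visit schedule (Protocol Appendix 1) and SAP 14.2.1 and 14.2.6.1 confirm it. Randomization comes at the end of Visit 2 (Protocol 8.1.5), so both scores precede it. SAP 9.3 defines baseline as the last non-missing pre-treatment value, so Visit 1 can enter the analysis only as a fallback when Visit 2 is missing. Neither document uses it as a covariate or says why it is left out.

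**The concern.** A single score on a 0 to 4 scale, whether an examiner's grade or a self-rating, is a noisy reading of a subject's usual level. A second pre-randomization reading can explain part of the Visit 6 variation that the first one misses. Because it is taken before randomization, adjusting for it cannot bias the treatment comparison.

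The trial succeeds only if both endpoints are significant for both doses (Protocol 10.4.4; SAP 9.5), and the plan itself puts the power for that at 66%. A small gain in each test compounds over four. At stake is some power, not the validity of the result.

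**Working it through.** **Inputs from the documents.** 45 completers per arm (50 randomized, 10% dropout). Sign: difference 0.5, SD of change 0.72. Symptom: difference 0.80, SD of change 1.15. Power is calculated "using a two-sample t-test at a significance level of 0.05". Protocol 10.4.1 adds: "All primary and secondary analyses will be 2-sided at a significance level of 0.05". No between-visit correlation is given.

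**Step 1: reproduce the plan's figures.** Noncentrality = difference / (SD × √(2/45)).
- Sign: 0.5 / (0.72 × 0.2108) = 3.29, power 90.3% (noncentral t). The plan states "90% power to detect a difference of 0.5 units between each of the active treatment groups" and placebo, which agrees.
- Symptom: 0.80 / (1.15 × 0.2108) = 3.30, power 90.4%. Agrees.
- Both endpoints: 0.9² = 81%. Both endpoints in both doses: 0.9⁴ = 65.6%, stated as 66%. Agrees under the plan's independence assumption.
- The doses share one placebo arm, so the two contrasts on an endpoint correlate at 0.5. With that, and endpoints still independent, power for all four tests is about 71% by simulation. This is the reference figure below.

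**Step 2: variance with and without Visit 1.** Let a = corr(V1,V2), b = corr(V2,V6), c = corr(V1,V6).
- Residual variance given Visit 2 is proportional to 1 − b².
- Given both visits it is proportional to 1 − R², where R² = (b² + c² − 2abc) / (1 − a²).
- Variance ratio = (1 − R²) / (1 − b²). With a = b = c = r it reduces to (1 + 2r) / (1 + r)².

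**Step 3: put in assumed correlations.**

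| Assumed pattern | Variance ratio | Variance cut | SE cut |
|---|---|---|---|
| c = a × b (Visit 1 adds nothing given Visit 2) | 1.000 | 0% | 0% |
| a = 0.6, b = 0.5, c = 0.4 | 0.979 | 2.1% | 1.0% |
| All equal 0.3 | 1.6 / 1.69 = 0.947 | 5.3% | 2.7% |
| All equal 0.5 | 2 / 2.25 = 0.889 | 11.1% | 5.7% |

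For the second row: R² = (0.25 + 0.16 − 0.24) / 0.64 = 0.266, and 0.734 / 0.75 = 0.979.

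A more realistic structure is a true score that decays over time plus measurement error. Take single-score reliability λ and true-score correlation ρ over 56 days, with 14 days between Visits 1 and 2. Then a = λρ^0.25, b = λρ, c = λρ^1.25. For λ from 0.6 to 0.9 and ρ from 0.6 to 0.9, the variance cut runs from about 1% to about 11%.

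**Step 4: power for all four tests.** The stated SDs are multiplied by the square root of the variance ratio, which treats them as residual SDs of the planned ANCOVA. Shared placebo arm, independent endpoints.
- Ratio 1.000: 71%
- Ratio 0.979: 72%
- Ratio 0.947: 75%
- Ratio 0.889: 79%

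The sample size sections describe 0.72 and 1.15 as SDs of the change from baseline. Read literally, with equal correlations r and equal variances at the visits, the residual SD of the planned ANCOVA is SD × √(1 − r²) / √(2(1 − r)). The planned model then already has all-four power of 93% (r = 0.3) or 87% (r = 0.5), with the four tests treated as independent. Adding Visit 1 moves these to 95% and 92%.

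**The case against.** The strongest reply is that nothing is wrong. ANCOVA on one baseline and site is valid and pre-specified, the power statement promises only that ANCOVA will do no worse than a t-test, and SAP 9.5 calls the trial primarily exploratory. All of that stands, and it is why this is an optional refinement.

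The second reply is that the gain may be close to nil. Visit 1 is further from Visit 6 than Visit 2 is. Fourteen days of open-label placebo drops lie between the two screening visits, and other topical drops need have stopped only 72 hours before Visit 1. Entry thresholds apply at both visits and restrict the range of scores. None of this affects validity, but it gives reason to expect c below b and weaker correlations throughout, hence a smaller gain. That also stands, and the range therefore starts at zero. Exactly zero is a special case, though: under simple decay it would need a Visit 2 score free of measurement error.

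Three stronger readings are tempting and are not supported:
- *That the gain could be far larger with strongly correlated scores.* Holding the SD of change at 1.15 with r = 0.7 and equal variances implies a discomfort SD of 1.15 / √0.6 = 1.48. On a 0 to 4 scale, subjects spread evenly over the five whole grades would have an SD of only 1.41, so a selected population is unlikely to reach 1.48.
- *That the study-eye rule makes the Visit 2 score especially noisy, so Visit 1 is worth more.* SAP 9.1 says that, when both eyes qualify, "the worst eye will be the eye with worse (higher) inferior corneal staining pre-CAE® at Visit 2". Staining drives that choice and discomfort only breaks ties, so the argument hardly reaches the symptom. For staining, simulations with two correlated eyes and r = 0.5 left the variance cut at about 10 to 11%, no higher than without selection.
- *That the change costs only one degree of freedom.* This is true of the ANCOVA. The imputation model runs by treatment and site, so the cost there is somewhat larger.

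**Conclusion.** The point holds as a modest missed efficiency. Both co-primary endpoints have a second pre-randomization score that is already collected, and the primary model does not use it. The planned analysis is unbiased and the 90%, 81% and 66% figures reproduce, so a reader should not infer an error in the model or a shortfall in the stated power.

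The size rests on correlations that the documents do not give. A fair range is 0 to 11% lower variance, or 0 to 6% lower standard error. All-four power goes from about 71% to between 71% and 79% if the stated SDs are residual SDs, the placebo arm is shared and the endpoints are independent. The top of the range needs Visit 1 to predict Visit 6 as well as Visit 2 does, which the run-in and the entry thresholds make unlikely. Severity: low, optional.

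**What to change.** Before unmasking, amend SAP 14.1.1 and 14.1.2, and note the change from Protocol 10.4.5 in SAP section 17:
- Add the study-eye Visit 1 pre-CAE score of the same endpoint as a second covariate in each primary ANCOVA. Keep Visit 2 as the baseline for the change score, so the quantity estimated does not change.
- Add the same score to the variable list of the imputation step, after checking that the cells can support it. With 3 sites there are nine treatment-by-site cells of about 150 / 9 ≈ 17 subjects. Going from two variables to three adds one mean, one variance and two covariances per cell.

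Cost: one model degree of freedom (135 completers, three arms, three sites and one covariate leave 129, falling to 128) and a few extra imputation parameters per cell. No new visit, measurement or subject is needed.

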10.4.6 Secondary Efficacy Analyses

The continuous and ordinal secondary efficacy variables collected at each visit will be summarized descriptively (n, mean, standard deviation, median, min and max) by visit and treatment group, and analyzed with two-sample t-tests comparing each of the active treatment groups to placebo. All visit-based data will be analyzed at each visit and change from baseline. Change scores from pre- to post-CAE® will be calculated as Post-CAE® score – Pre-CAE® score. A Wilcoxon rank sum test and an ANCOVA model adjusting for baseline and site will also be assessed where appropriate. No imputation will be performed for secondary efficacy variables.

Fluorescein staining by region and total, lissamine green staining by region, TFBUT, conjunctival redness, unanesthetized Schirmer's test, drop comfort assessment, OSDI, ocular discomfort and dry eye symptoms, ocular discomfort during CAE®, pre- to post-CAE® changes, and changes from baseline in these measures will be analyzed by visit using two-sample t-tests and Wilcoxon rank sum tests, as appropriate.

The worst symptom for each subject will be identified as the symptom with the highest average score during the run-in period (Days -14 to -1) as recorded in the subject diary. The worst symptom and each individual symptom will be analyzed per day using a two-sample t-test. Additionally, the average score for the worst symptom and each individual symptom will also be analyzed separately using a Wilcoxon rank sum test.

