5 STUDY POPULATION

5.1 NUMBER OF SUBJECTS

It is estimated that approximately 375 subjects will be screened to enroll approximately 150 randomized subjects (50 in each arm). Subjects will be randomized in a 1:1:1 ratio of HL036 Ophthalmic Solution (0.25%) to HL036 Ophthalmic Solution (0.1%) to HL036 Vehicle Ophthalmic Solution.

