#### 14.2.1 FLUORESCEIN STAINING

Corneal and conjunctival fluorescein staining will be performed at all scheduled visits, on both eyes and graded using the Ora Calibra® Corneal and Conjunctival Staining Scale. Both pre- and post-CAE® assessments will be made at Visits 1, 2, 4, 5, and 6. The scale will grade the cornea and conjunctiva by five regions: inferior, superior, central, temporal, and nasal. The Ora Calibra® Corneal and Conjunctival Staining Scale ranges from 0 to 4 [REDACTED], where grade 0 = none, [REDACTED] and 4 = severe.

Fluorescein staining scores will be summarized by visit, time point (pre- and post-CAE®), and region (5 regions, plus corneal sum, conjunctival sum, and total scores) for the study eye using quantitative summary statistics. The corneal sum score will be the sum of scores from the inferior, superior, and central regions. The conjunctival sum score will be the sum of scores from the nasal and temporal regions. The total score will be the sum of scores from all five regions.

Pairwise two-sample t-tests will be employed to compare treatment and placebo means at each visit and time point. Comparisons between treatment groups and between all active groups and placebo will also be conducted. The differences in means, two-sided 95% confidence intervals (CIs) for the difference in means and p-values will be reported. Wilcoxon rank sum tests will also be conducted. Analyses will be performed on the ITT population with observed data only.

Changes from baseline will be compared between treatment groups using ANCOVA models that adjust for baseline and site. The differences in means, two-sided 95% confidence intervals (CIs) for the difference in means and p-values will be reported. T-tests and Wilcoxon rank sum tests will also be conducted. Analyses will be performed on the ITT population with observed data only.

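### Most secondary endpoints get five p-values per contrast and no lead test; the baseline- and site-adjusted ANCOVA already planned should be named as the result

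*Protocol*

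**What the plan says.** **Protocol 10.4.6** has the continuous and ordinal secondary variables analyzed by two-sample t-tests of each active group against placebo, and then adds: "A Wilcoxon rank sum test and an ANCOVA model adjusting for baseline and site will also be assessed where appropriate". It gives no criterion for when ANCOVA is appropriate. Its second paragraph assigns only t-tests and Wilcoxon tests to the listed measures and their changes from baseline. Protocol 10.4.1 sets the level: "All primary and secondary analyses will be 2-sided at a significance level of 0.05".

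**SAP 14.2.1 (fluorescein staining)** starts with the score itself: "Pairwise two-sample t-tests will be employed to compare treatment and placebo means at each visit and time point". Wilcoxon tests on the score follow. It then turns to change: "Changes from baseline will be compared between treatment groups using ANCOVA models that adjust for baseline and site". T-tests and Wilcoxon tests on change are added to that. This makes five p-values for one contrast at one visit and time point. The pattern recurs for lissamine green staining, TFBUT, redness, Schirmer's test, ocular discomfort before and after CAE, the symptom questionnaire, the diary, the VAS and the OSDI.

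Three sections differ:
- Drop comfort (SAP 14.2.10) has two tests.
- Tear mediators (14.2.12) have two, on percent change.
- Discomfort during CAE (14.2.6.2) has seven: two on the score, two on change from minute 0, and three on change from baseline.

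**Coprimary sections.** Here the tests are ranked. Protocol 10.4.5 calls the t-tests and Wilcoxon tests supportive, and SAP 14.1.1 and 14.1.2 call them sensitivity analyses beside the ANCOVA. SAP 14.2 has no such sentence.

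**Which document governs.** SAP 1 says that its methods supersede the protocol's. SAP 17 says that nothing has changed from the protocol.

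**The concern.** For one endpoint, dose and visit, the reader of the study report will see up to five p-values, and the plan does not say which one answers the question. Two things can follow.

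First, the most favourable value can be quoted, so the error rate attached to a significant secondary result is no longer 5%. Second, someone who follows the protocol's order will read the unadjusted t-test. That test ignores the baseline score and the site, although randomization blocks are distributed by site and the primary model uses both.

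The stake is how the secondary results are interpreted. SAP 3.2 also lists inferior staining and ocular discomfort at all time points among the secondaries, so the two coprimary measures at Day 57 are retested, on observed data, within this unranked set.

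**Working it through.** **Inputs from the documents**
- Two-sided 0.05 for secondary tests (Protocol 10.4.1).
- 45 completers per arm (Protocol 10.3). "Subjects will be randomized in a 1:1:1 ratio" (Protocol 5.1).
- Sign: "fluorescein staining of 0.72 units, a sample size of 45 subjects per group will have 90% power to detect a difference of 0.5 units".
- Symptom: "A sample size of 45 subjects per treatment arm will have 90% power to detect a mean difference of 0.80 units", "assuming a standard deviation of 1.15 units".
- Up to 3 sites (Protocol synopsis).

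**Assumed, because the documents do not give them:** the correlation ρ between baseline and visit score (0.3, 0.5, 0.7) and a secondary effect of 0.5 SD on the visit value.

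**1. The plan's own figures reproduce.** With noncentrality = (difference/SD) × √(45/2) and 88 degrees of freedom:
- Sign: 0.5/0.72 = 0.694; 0.694 × 4.743 = 3.29; power 90.3%.
- Symptom: 0.80/1.15 = 0.696; 0.696 × 4.743 = 3.30; power 90.4%.
- 0.9² = 81% and 0.9⁴ = 66%, as stated.

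The documents give no power or error figure for the secondary endpoints.

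**2. Chance under no effect that at least one of the five tests has p < 0.05.** Simulation of one dose-placebo contrast at one visit, with 45 per arm and three sites; the ANCOVA is fitted to all three arms; 60,000 trials per cell.

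| Outcome scale | ρ = 0.3 | ρ = 0.5 | ρ = 0.7 |
|---|---|---|---|
| Normal | 10.7% | 11.4% | 11.7% |
| 0 to 4 in half steps | 10.6% | 10.9% | 11.5% |
| 0 to 4 in whole steps | 10.5% | 10.6% | 11.0% |
| Half steps, assumed entry floor on baseline | 9.9% | 10.2% | 10.8% |

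Each test alone stays close to 5%; ANCOVA is between 4.8% and 5.1% in every cell. Five independent tests would give 1 − 0.95⁵ = 22.6%. That is only an upper reference, because the five tests share the same data.

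**3. Power by choice of test.** On normal data, relative to the SD of the visit score, the residual SD is 1 for the visit-value t-test, √(2(1 − ρ)) for the change t-test and √(1 − ρ²) for ANCOVA. For a 0.5 SD effect the noncentrality is 0.5 × 4.743 divided by that factor:
- Visit-value t-test: 2.37, power 65%.
- Change t-test: 2.00, 2.37 and 3.06 at ρ = 0.3, 0.5 and 0.7; power 51%, 65% and 86%.
- ANCOVA: 2.49, 2.74 and 3.32; power 69%, 78% and 91%. These are slight overestimates, because they ignore the cost of chance imbalance in baseline. Simulation gives 67% to 69%, 76% to 77% and 89% to 91%.

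So the gap between ANCOVA and the visit-value t-test is a few points at ρ = 0.3, about 11 at 0.5 and about 25 at 0.7.

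**4. The same comparison at the plan's design effect.** If 0.694 SD is taken as the effect on the visit value, the visit-value t-test has 90%, and ANCOVA has 93%, 96% to 97% and 99.5%. The gap is then about 3 to 10 points, because power is already near its ceiling.

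**The case against.** The strongest reply is that the SAP governs and already runs the better model. For change from baseline it puts ANCOVA first and reports the difference, confidence interval and p-value. A reader might infer that the plan itself gives up power. The documents do not support that: power is lost only if a t-test is read as the result. This stands, and the point is limited accordingly. What remains is that the SAP's order is not a designation, and that SAP 17 claims no departure from a protocol whose main secondary test is the t-test.

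Further limits also stand:
- A reader might say that the error rate more than doubles. With half-step scores and an entry floor it is just under double at ρ = 0.3, so about double is as far as the calculation goes.
- A reader might take five tests as the count for every endpoint. It fits most, but not drop comfort, tear mediators or discomfort during CAE. The protocol sentence itself names three methods.
- A reader might suppose that these results will fix the dose and endpoint of the next trial. Neither document says so.
- SAP 9.5 calls the trial primarily exploratory, and no secondary p-value enters the success rule.

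Exploratory status can justify leaving results unadjusted across endpoints. It does not settle which p-value is the result for one endpoint, and the plan still tests secondaries at 0.05.

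It can also be said that a normal-theory model is only a preference for short ordinal scales. In the check above, ANCOVA kept its 5% level on discrete scores, and the Wilcoxon tests stay in the report as support.

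**Conclusion.** The point holds as a gap in designation. For most secondary endpoints the SAP yields five unranked p-values per contrast, visit and time point. Reading any of them as the result raises the per-contrast false-positive rate to roughly 10% to 12%, about double nominal. Reading the visit-value t-test instead of ANCOVA lowers power: about 65% against 76% for a 0.5 SD effect at ρ = 0.5, with a small gap at 0.3 and a larger one at 0.7.

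The correlation and the 0.5 SD effect are assumptions. The error result depends little on the correlation; the power gap depends on it strongly. Both figures concern a single contrast, before regions, visits, doses and the pooled-active comparison are counted.

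The coprimary conclusions are untouched, because ANCOVA is the named analysis there. The change is worth making because it removes the choice among p-values within each contrast at almost no cost.

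**What to change.** In Protocol 10.4.6 (and the matching synopsis text) and in SAP 14.2, state that for visit-based and diary secondary endpoints with a baseline, the ANCOVA on change from baseline, adjusted for baseline and site, is the single lead analysis. With baseline in the model, the treatment difference is the same whether the outcome is the visit score or the change, so one model serves both.

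Label the t-tests and Wilcoxon tests as supportive, as the coprimary sections do, and delete the where-appropriate qualifier. Exempt drop comfort, which has no baseline, and tear mediators, which are analyzed as percent change with no ANCOVA planned; both keep the t-test as lead.

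The cost is a few sentences. Every model needed is already in the SAP, and no new data are required. The change does not control multiplicity across endpoints, regions, visits and doses, so the text should also say that secondary p-values remain exploratory.
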